7.3. Protocol Deviations

A full list of protocol deviations will be compiled and reviewed by the clinical team to identify Important versus non-important protocol deviations before the primary analysis and before the final database lock. For deviations at study entry, patients will be assessed against the inclusion and exclusion criteria of the protocol. For on-study deviations, compliance with the protocol will be examined using blinded review of the database regarding prohibited therapies, and timing and availability of planned assessments.

Patients having important protocol deviations will be summarized using counts and percentages by deviation category and coded deviation term based on the Full Analysis Set for Main Study and will be re-generated at final analysis including protocol deviations occurring during the Extension Study.

A listing of all protocol deviations will be provided with treatment period flag (Main Study or Extension Study). Important protocol deviations will be flagged in the listing.

7.4. Demographic and Baseline Characteristics in Main Study

The following demographic and baseline characteristics will be summarized by treatment group, as well as overall, for Randomized Analysis Set:

- Age in years and by age group (21-<65, >=65)
- Gender
- Race
- Ethnicity
- Height (cm), weight (kg), weight group, body mass index (kg/m^2), body mass index (BMI) group (< 25, 25 -< 30, $\geq 30 \text{ kg}/\text{m}^2$), waist and hip circumferences (cm) and waist to hip ratio
- Systolic and diastolic blood pressure (mmHg)
- Randomization factors (T2DM status and fibrosis stage)
- Screening HbA1C $\geq 6.5\%$ (Yes/ No)
- Baseline HbA1C $\geq 6.5\%$ (Yes/ No)
- Fasting plasma glucose $\geq 126 \text{ mg}/\text{dL}$ (Yes/ No)

- Liver biopsy results (fibrosis stage, steatosis score, ballooning degeneration score, lobular inflammation score, NAS)
- MRI-PDFF ($\geq 8\%$), cT1, ELF > 9.8 (Yes/No), Fibroscan VCTE kPa and CAP score
- ALT, Pro-C3, Adiponectin, serum triglycerides, HDL-c, Non-HDL-c, LDL-c, HBA1c.
- Estimated Glomerular Filtration Rate (eGFR) category (normal: ≥ 90 mL/min/1.73m²; mild Renal Impairment: 60-89 mL/min/1.73m²; moderate Renal Impairment: 30-59 mL/min/1.73m², and severe Renal Impairment: 15-29 mL/min/1.73m²)
- History of hypertension
- History of lipid disorder
- History of obesity
- History of menstrual disorder (for females)
- History of COVID-19 and complications.

7.5. Medical History

General medical history and background therapy will be summarized at primary analysis by treatment group, as well as overall, for FAS population and presented in a by-subject listing.

Medical history will be coded using the Medical Dictionary for Regulatory Activities (MedDRA) Version 24.0 or higher.

7.6. Prior and Concomitant Medication/Procedure

Medications will be coded using World Health Organization-Drug dictionary (WHO-DD), March 2021 or later.

The frequencies of use of prior/ concomitant medications will be summarized by treatment group for FAS according to Anatomical Therapeutic Chemical (ATC) class and preferred term.

Prior and concomitant medications/ procedure will be listed for each subject.

7.7. Extent of Exposure and treatment compliance

The length of exposure, number of actual drug doses and number of missed doses, total dose administered (mg), and study treatment compliance will be summarized by actual treatment group for the Main Study and for the Entire Study.

The IP administration and compliance data, including reasons for poor compliance, will be listed.

Main Study

Length of Main Study exposure in days will be derived as:

- Length of Main Study exposure (days) for QW dosing = (date of last dose in Main Study) – (date of first dose in Main Study) + 7;
- Length of Main Study exposure (days) for Q2W dosing = (date of last dose in Main Study) – (date of first dose in Main Study) + 14.

Total dose administered (mg) in Main Study will be calculated as number of doses received x dosage (mg) of the investigational product contained in each dose.

The Main Study compliance = (total doses administered in Main Study /total doses expected in Main Study) x 100%. Total doses expected is defined as the total number of doses protocol defined until the end of Main Study treatment. If the dose of a kit is not fully administrated, the dosage will be imputed as 0 mg for the kit.

Entire Study

The overall length of exposure (days), total dose administrated (mg), and the overall study compliance will be derived following the same logic as Main Study by the actual treatment subject received. For subjects who switched the treatment at the Extension Study, the length of exposure (days), the total dose administrated (mg), and the study compliance will be derived for placebo and pegozafermin 30mg respectively. Column “Placebo (main) and pegozafermin 30 mg QW (Extension)” will report both study drugs.

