Subjects completing the Main study will continue for an additional 24 weeks in the Extension study. The Extension study will commence at Main study Week 24 visit. At Week 24, subjects randomized to placebo QW in the Main study will be re-randomized 1:1 to pegozafermin 30 mg QW (n=21) or placebo QW (n=21) and receive the re-randomized treatment beginning at the Week 26 visit (which may be an in-clinic or a remote home visit). All other subjects will continue to receive the same treatment regimen in the Extension study that they received during the Main study. IP will be administered over 24 additional weeks (includes 24 administrations in QW dose regimen and 12 administrations in Q2W dose regimen), for approximately 48 weeks of treatment over the entirety of the study (Main and Extension). In the Extension study, specifically-identified Sponsor personnel will not be blinded; however, subjects, investigators and site staff will remain blinded to IP (placebo or pegozafermin). Dose regimen (QW or Q2W) will be known to all parties in the Extension study.

Number of Subjects and Intervention Groups

A total of approximately 184 subjects are planned in the Main study as follows:

Treatment Group	Dose	Frequency	Route of Administration	Number of subjects
Placebo	-	QW	SC	42*
Placebo	-	Q2W	SC	22
Pegozafermin	15 mg	QW	SC	16
Pegozafermin	30 mg	QW	SC	64
Pegozafermin	44 mg	Q2W	SC	40

Abbreviations: QW, weekly; Q2W, every 2 weeks; SC, subcutaneously

* At Week 24, subjects randomized to placebo QW in the Main study will be re-randomized 1:1 to pegozafermin 30 mg QW (n=21) or placebo QW (n=21)

Study Duration

For each subject, the total duration of study participation will be up to approximately 112 weeks:

Screening Period: Up to 12 weeks, which may be extended with Sponsor's approval

Main Study 24 weeks (includes 24 administrations in QW dose regimen and

Treatment Period: 12 administrations in Q2W dose regimen)

Extension Study 24 weeks (includes 24 administrations in QW dose regimen and

Treatment Period: 12 administrations in Q2W dose regimen)

Extension Study

Follow-up Period: Approximately 4 weeks from last dose of IP.

Immunogenicity Approximately [REDACTED] from last dose of IP

[figure not shown]
Follow-up Period

Data Monitoring Committee: Yes

An independent DMC will periodically review overall unblinded safety data per DMC charter.

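### SAP 7.7 counts a partly given kit as 0 mg, which understates total dose administered whenever some drug was injected

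*SAP*

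**What the plan says.** SAP 7.7 (Extent of Exposure and treatment compliance) plans a descriptive summary: "total dose administered (mg), and study treatment compliance will be summarized by actual treatment group". For the Main Study, total mg is "calculated as number of doses received x dosage (mg) of the investigational product contained in each dose". The next paragraph defines compliance as a ratio of dose counts, "The Main Study compliance = (total doses administered in Main Study /total doses expected in Main Study) x 100", and ends with the rule for incomplete kits: "If the dose of a kit is not fully administrated, the dosage will be imputed as 0 mg for the kit". The Entire Study summaries follow the same logic. The section also plans a listing: "The IP administration and compliance data, including reasons for poor compliance, will be listed".

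The SAP does not define when a kit counts as fully administered. It does not say whether the 0 mg value enters the mg total, the compliance ratio or both. Nor does it say whether a partly given dose is a dose received or a missed dose.

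**The concern.** An imputation normally stands in for an unknown value. Here the one thing known about the record is that some drug went in, and 0 mg is the one value that is certainly wrong. The error always has the same sign. It also weighs more on the two-weekly arm, where each dose is one twelfth of the Main Study total rather than one twenty-fourth.

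At stake is the accuracy of the exposure table, which readers will set beside the safety results. The plan itself foresees partial dosing: the PK Analysis Set definition (Protocol 9.3, SAP 6) names an incomplete dose as an event that can spoil PK results. Protocol 6.1 and 6.2 place many administrations at home, given by the subject or a caregiver.

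**Working it through.** The documents state no total-mg or compliance figure, so there is nothing to reproduce. What follows is direct arithmetic.

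**Inputs from the documents**
- Planned Main Study administrations: 24 weekly or 12 two-weekly (SAP 3.2). The Schedule of Activities agrees: Day 1 plus Weeks 1 to 23 is 24 doses, and Day 1 plus every second week from 2 to 22 is 12.
- Dose levels: 15 mg weekly, 30 mg weekly, 44 mg two-weekly.

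**Assumptions (not in the documents)**
- One kit per dose. Protocol 6.4.2 allows for more than one kit number, and the vial strength is redacted.
- k = 1 partial dose per subject, with k = 3 as a heavier case. The fraction f of that dose actually given runs from 10% to 90%.

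**Formulas**, for N planned doses of d mg
- Amount given: d(N − k) + k·f·d
- Total under the 0 mg rule: d(N − k)
- Relative error: −k·f / (N − k + k·f). The dose d cancels, so both weekly arms have the same percentage error.

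**One partial dose**

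| Arm | f | Given (mg) | 0 mg rule (mg) | Error |
|---|---|---|---|---|
| 30 mg weekly | 10% | 693 | 690 | −0.4% |
| 30 mg weekly | 50% | 705 | 690 | −2.1% |
| 30 mg weekly | 90% | 717 | 690 | −3.8% |
| 44 mg two-weekly | 10% | 488.4 | 484 | −0.9% |
| 44 mg two-weekly | 50% | 506 | 484 | −4.3% |
| 44 mg two-weekly | 90% | 523.6 | 484 | −7.6% |

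For example, the 44 mg arm at 90% gives 11 × 44 + 0.9 × 44 = 523.6 mg against 11 × 44 = 484 mg, and 484/523.6 − 1 = −7.6%. For 15 mg weekly with half of one dose given, the totals are 352.5 mg and 345 mg, again −2.1%.

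**Three half-given doses**
- 30 mg weekly: 630 against 675 mg, −6.7%.
- 44 mg two-weekly: 396 against 462 mg, −14.3%.

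**Compliance, one partial dose**
- Counted as not administered: 23/24 = 95.8% weekly, 11/12 = 91.7% two-weekly.
- Counted as administered: 100% in both.

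The SAP does not say which of these two is meant.

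**The case against.** Three arguments tell against making much of this.

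First, 0 mg may be a deliberate conservative convention for records where the amount is unknown. That is reasonable for a compliance count, where a dose is either complete or not. It is weaker for total mg, because the rule as written applies even when the amount given is known.

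Second, the effect is small and confined. SAP 7.10.1 tabulates adverse events as subject incidence by treatment group, no safety analysis is specified by mg, and the administration data are listed. Protocol 6.1 also accepts a 5% tolerance on each dose for withdrawal from the vial and calls it negligible. One half-given dose moves a subject's total by less than that; three exceed it in every arm. The tolerance concerns drawing up a dose, however, and does not justify removing a whole kit. The point that the effect is limited stands in full.

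Third, the remedy depends on the amount being captured. The case report form is not among the documents, so this cannot be confirmed, and the fix must cover records with no amount.

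Two stronger readings are tempting, and the documents support neither.

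- A reader might infer that the product formula and the 0 mg rule contradict each other, so that the same record is misstated upward or downward. They stand in consecutive paragraphs and read naturally as a general formula with a specific exception. On that reading the error is downward only. Overstatement needs a different reading, in which the 0 mg rule is confined to compliance and the partial dose still counts as received in full. Any single reading errs in one direction.
- A reader might infer that fully adherent subjects who switch from placebo to pegozafermin would show 26/24 = 108% and 22/24 = 92% compliance. The SAP does not set 24 as the denominator for each drug. Expected doses are those the protocol schedules, and for switchers "the study compliance will be derived for placebo and pegozafermin 30mg respectively". These subjects "receive the re-randomized treatment beginning at the Week 26 visit", and weekly dosing runs to Week 47. That already gives 26 placebo doses (Day 1 and Weeks 1 to 25) and 22 pegozafermin doses (Weeks 26 to 47), hence 100% for each.

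**Conclusion.** The concern holds as a minor error in a stated rule. Wherever the 0 mg imputation feeds total dose administered, it understates exposure for any subject who received part of a kit. With one kit per dose and one partial dose of 10% to 90%, the range is 0.4% to 3.8% of the Main Study total for weekly dosing and 0.9% to 7.6% for two-weekly dosing. These are errors for an affected subject, not for an arm mean. The effect on a group summary depends on how often partial doses occur, which the documents do not give. With several kits per dose, only the incomplete kit's mg is lost and the error shrinks.

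The consequence is limited to the descriptive exposure and compliance summaries. The efficacy analysis does not use them.

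**What to change.** In SAP 7.7, for total dose administered (mg), replace the 0 mg imputation with the amount recorded as administered. Where no amount is recorded, report the partial dose in a separate count and show the subject's total with that kit at 0 and at full dose, as lower and upper bounds. If the 0 rule is kept, state that it applies only to the compliance count, so that a partly given dose is not counted as administered there.

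The cost is a few lines of SAP text and one extra derivation, with bounds in place of a single figure for the affected subjects. No new visits or design changes are needed. Naming 26 placebo and 22 pegozafermin expected doses for switchers would be a helpful clarification but is optional.

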7.8. Efficacy Analysis for Main Study

The primary efficacy endpoints are (1) proportion of subjects with NASH resolution without worsening of fibrosis at Week 24 compared to baseline (2) proportion of subjects achieving improvement of fibrosis ≥ 1 stage without worsening of NASH at Week 24 compared to baseline. The following hypothesis will be tested for each primary endpoint:

- The null hypothesis: there is no difference in the proportion of subjects meeting the primary endpoint between the placebo and each pegozafermin dose group.
- The alternative hypothesis: the proportion of subjects meeting the primary endpoint between the placebo and each pegozafermin dose group is different.

The study will be considered successful if a given pegozafermin dose group is demonstrated to be superior to the placebo group in either of the two primary endpoints at 0.05 significance level.

Estimand Framework

As detailed in the ICH E9 (R1) addendum, the following five attributes will define the estimand framework in this trial. The primary estimand will be defined as a treatment policy (TP) estimand, which compares treatment outcomes in two randomized arms at 24 weeks post-randomization irrespective of what changes in treatment could have occurred post-randomization as a result of various intercurrent events (ICE). To implement TP strategy, it will be important that outcomes are collected and recorded after occurrence of ICE's as close to the 24 week time point, regardless of what actual treatment the patient may be receiving. Below are the 5 attributes of the primary estimand:

- Treatment conditions: Randomization to Pegozafermin (15 mg QW or 30 mg QW or 44 mg Q2W) or Placebo, regardless of ICE's and deviations from the randomized treatment and actual treatment received during or at the end of the treatment period.
- Population: Randomized subjects with fibrosis stage 2 or 3 and NAS ≥ 4 at baseline per 3-panel consensus read who received at least 1 dose of IP.
- Endpoints: NASH resolution without worsening of fibrosis at Week 24 compared to baseline; improvement of fibrosis ≥ 1 stage without worsening of NASH at Week 24 compared to baseline
- Intercurrent events (ICEs): Three types of ICEs are defined below.
- Population-level summary: Between treatment group difference expressed in terms of the percentage differences in achieving the endpoints.

The following types of ICEs will be documented in course of the study.

- ICE-1: Discontinuation of treatment due to lack of efficacy.
- ICE-2: Discontinuation of treatment due to adverse events (AE).
- ICE-3: All other events, i.e., protocol deviation, etc.

The primary analysis will use all observed outcomes at Week 24, regardless of actual treatment. All outcomes collected from patients experiencing this ICE after the actual ICE will be used in the analysis and missing values resulting from any ICE will be imputed assuming an imputation model informed by observed outcomes from similar patients with this type of ICE. The imputation model will include terms for the randomized treatment arm and the type of ICE(s) experienced by patients with missing outcomes, i.e., ICE-1,2,3 (as defined above) or None. The final inference following multiple imputation (MI) will be conducted using Rubin's combination rules.

Although the ICEs' defined above will be all handled by the same treatment policy strategy for the primary estimand, various sensitivity analyses (SA) will be conducted that will incorporate different strategies, depending on the type of ICE. For the purposes of sensitivity analysis, patients who experienced any of the listed ICEs (ICE-1,2,3), the outcomes for the primary efficacy endpoint will be considered missing starting from the occurrence of each ICE (even if outcomes are collected following an ICE) and then the missing outcomes will be imputed using appropriate imputation strategies.

For ICE-1, the SA will use the "return to baseline" hypothetical strategy, implying no benefits have been received for such patients from randomization until the end of the treatment period. The missing outcomes will be imputed using a relevant regression model fitted to the baseline data within each treatment arm with patient age, gender, baseline NAS score and stratification factors included as covariates.

For ICE-2, SA will be handled with the "control-based" hypothetical strategy implying that patients would have switched to the control treatment (i.e., placebo) starting from the occurrence of ICE-2 to the end of the treatment period. The missing outcomes will be imputed from a similar regression model fitted to the placebo arm alone with patient age, gender, baseline NAS score and stratification factors as covariates.

For ICE-3, SA will be handled using a hypothetical strategy that assumes that patients would have continued their assigned treatment starting from ICE-3. The missing outcomes will be imputed using the same model as for ICE-2 but fitted to each respective treatment arm.

Missing data due to reasons unrelated to the intercurrent events (ICE-1, 2, 3), e.g., missingness caused by study termination by sponsor, will be imputed using the same model as for ICE-3.

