6.7.1. Prohibited Medications/Therapies

Prohibited therapies include:

- Bariatric surgery
- Elective bone surgery for any bone disorders
- Medications historically associated with secondary NAFLD requiring >2 weeks of pharmacologic dosing . These include amiodarone, methotrexate, glucocorticoids,

tetracyclines, tamoxifen, estrogens or anabolic steroids at doses greater than those used for hormone replacement.

- Other hepatotoxic agents including but not limited to, nefazodone, isoniazid, valproate, and carbamazepine.
- The TNF (tumor necrosis factor) antagonists, adalimumab, etanercept and certolizumab, infliximab or sulfasalazine are prohibited during the Main Study but may be considered for managing emerging AEs in the Extension Study.
 - Short-term oral steroid bursts with/without taper as well as topical and inhaled corticosteroids are allowed.
- Antidiabetic medications: Thiazolidinediones (e.g., pioglitazone) are prohibited throughout study to minimize risk of confounding effect with pegozafermin treatment. Dose adjustments or switching from one medication to another within the same drug class are allowed after randomization for DPP-IV inhibitors (“gliptins”), SGLT2 inhibitors (“gliflozins”) and GLP-1 agonists (“glutides”, including semaglutide [Ozempic]); However, initiation of new DPP-IV inhibitors, SGLT2 inhibitors, or GLP-1 agonists is not allowed during screening and the Main Study (e.g., switching from a DPP-IV inhibitor to a GLP-1 agonist is not allowed, but switching from one DPP-IV inhibitor to another DPP-IV inhibitor is allowed). Initiation of these agents for uncontrolled hyperglycemia (but not for weight loss) may be allowed during the Extension Study with the Medical Monitor’s approval.
- Vitamin E (> 400 IU/day) should not be initiated, or dose increased during the study.
- Any investigational product, FGF21 analogs (e.g., LY2405319, LY3025876, BMS-986036, BMS-986171, PF-05231023, AKR-001, pegozafermin), or FGFR1-activating products. Note: study participants will not be allowed to participate in other interventional trials for FGF21 analog or FGFR1 activating products, during the immunogenicity follow up period.
- Weight loss medications (including GLP-1 agonists specifically for weight loss) should not be initiated during the study.

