7.8.1.1. Primary analysis

The primary analysis will be carried out using an MI-based strategy that includes the following three steps:

- Step 1. Missing outcomes will be imputed a large number of times ($M=100$) using PROC MI based on the model outlined in Table 5 based on a logistic regression model.
- Step 2. The Cochran-Mantel-Haenszel (CMH) test stratified by T2DM status (yes vs. no) and fibrosis stage (F2 vs. F3) will be applied to each completed data set to compare the proportions of responders at Week 24 between each pegozafermin group and placebo, adjusting for the stratification factors. The point estimates and associated standard errors for the differences in proportions as well as CMH test statistics will be calculated.
- Step 3. The CMH summaries from individual completed sets will be combined using Rubin’s rules to produce a single inferential statement (treatment effect, standard error, 95% confidence interval and p-value) via PROC MIANALYZE.

Note that a patient can have only one ICE (classified as ICE-1, -2, -3) or none (0). Once an ICE of specific type has occurred, the status of ICE variables remains fixed at that value until the end of the trial. All collected data are used in imputation. Imputation is done by the trial arm (TRT) but, if the data are sparse, instead of imputing by TRT, include TRT as covariate.

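### ICE-3 has no stated limits and the ICE code is fixed once set; read literally, the per-ICE sensitivity analysis can discard observed biopsies and mask later discontinuations

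*SAP*

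**What the plan says.** SAP 7.8 (Estimand Framework) lists three intercurrent events. The first two are treatment discontinuations: ICE-1 for lack of efficacy, and "ICE-2: Discontinuation of treatment due to adverse events (AE"). The third is "ICE-3: All other events, i.e., protocol deviation, etc". Protocol 9.1.1 uses the same wording.

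SAP 7.8.1.1 adds two coding rules: "Note that a patient can have only one ICE (classified as ICE-1, -2, -3) or none (0"), and "Once an ICE of specific type has occurred, the status of ICE variables remains fixed at that value until the end of the trial".

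The code is used in two ways.

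- **Primary analysis.** "The primary analysis will use all observed outcomes at Week 24, regardless of actual treatment". ICE type enters only the model that imputes missing outcomes. Table 5 allows it to be dropped if most subjects with an ICE have no outcome.
- **Per-ICE sensitivity analysis (7.8, Table 5, 7.8.1.2.1).** Outcomes "will be considered missing starting from the occurrence of each ICE (even if outcomes are collected following an ICE"). ICE-1 is then imputed by return to baseline, ICE-2 from placebo, and ICE-3 from subjects in the same randomized arm who had no ICE.

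SAP 7.3 has the clinical team review all deviations to "identify Important versus non-important protocol deviations before the primary analysis". That review covers both prohibited therapies and the timing of assessments. Protocol 6.7.1 is the source for prohibited therapies; for example, "initiation of new DPP-IV inhibitors, SGLT2 inhibitors, or GLP-1 agonists is not allowed during screening and the Main Study". The ICE-3 definition does not refer to the 7.3 classification.

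**The concern.** As worded, ICE-3 puts the start of a prohibited GLP-1 agonist and an out-of-window visit in the same class. In the per-ICE sensitivity analysis both lead to the same step: an observed Week 24 biopsy is replaced by an imputed one. For the prohibited drug that is the purpose of the analysis. For a late visit by a fully dosed subject it discards good data.

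The single fixed code adds a second problem. A subject with a deviation in Week 3 who stops for an AE in Week 8 stays ICE-3. On active drug, that subject is then imputed as if treatment had continued, not by the control-based rule written for AE discontinuation. A later stop for lack of efficacy is masked in the same way.

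In the primary analysis, the same coding would put subjects who stopped treatment for other reasons, or for an AE after an earlier deviation, in one imputation category with fully treated subjects who had only a minor deviation.

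What is at stake is the meaning of the one planned analysis that sets aside outcomes after a prohibited therapy. Two programmers could also code ICE-3 very differently from the same text.

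**Working it through.** **1. The plan's own power figures.** Inputs from SAP 3.5: response 15% vs 45% (NASH resolution) and 20% vs 50% (fibrosis improvement); 64 vs 64 (30 mg QW vs placebo) and 40 vs 64 (44 mg Q2W vs placebo); 15% dropout; two-sided 0.05. For equal arms of n, with p̄ the mean of p1 and p2:

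power = Φ{[(p2 − p1) − 1.96·√(2p̄(1 − p̄)/n)] / √([p1(1 − p1) + p2(1 − p2)]/n)}

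NASH resolution, 30 mg QW, n = 64 × 0.85 = 54.4: (0.30 − 1.96 × 0.0879)/0.0830 = 1.54, so power is 93.8%. The four comparisons give 93.8, 91.8, 87.1 and 84.0%, against the stated 94, 92, 87 and 83%. The plan's figures reproduce to within about one point.

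**2. Biopsies set aside in the per-ICE sensitivity analysis.** Let f be the share of evaluable biopsies with an earlier ICE-3, equal in both arms. The documents do not give f, so it is an assumed range. Imputing from same-arm subjects without an ICE is treated as roughly equal to losing the observation, so n becomes 54.4 × (1 − f), and likewise 34 × (1 − f) for 44 mg Q2W.

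| f | 30 mg, NASH | 30 mg, fibrosis | 44 mg, NASH | 44 mg, fibrosis |
|---|---|---|---|---|
| 0 | 93.8% | 91.8% | 87.1% | 84.0% |
| 0.10 | 91.2% | 88.8% | 83.5% | 80.0% |
| 0.20 | 87.6% | 84.8% | 79.0% | 75.2% |
| 0.30 | 82.9% | 79.6% | 73.6% | 69.5% |
| 0.50 | 68.5% | 64.8% | 59.2% | 55.1% |

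Primary-analysis power does not change by this route, because observed biopsies stay in.

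**3. AE stops coded as ICE-3.** Let a be the share of the 30 mg arm stopping for an AE and q the share of those with an earlier ICE-3 (both assumed). On the plan's NASH-resolution rates, ICE-2 coding imputes at 15% and ICE-3 coding at 45%:

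arm rate = (1 − a) × 0.45 + a × [(1 − q) × 0.15 + q × 0.45]

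| a | q = 0 (all coded ICE-2) | q = 0.5 | q = 1 |
|---|---|---|---|
| 5% | 43.5% | 44.25% | 45.0% |
| 10% | 42.0% | 43.5% | 45.0% |
| 15% | 40.5% | 42.75% | 45.0% |

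At a = 10% the rate is 1.5 points too high with q = 0.5 and 3.0 points with q = 1. Each masked subject adds 0.30/64 = 0.47 points. On placebo, both rules draw on placebo subjects without an ICE, so for AE stops the shift is one-sided and favours pegozafermin.

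For scale, the standard error of the difference at 54 per arm is √[(0.15 × 0.85 + 0.45 × 0.55)/54] = 8.3 points, so 1.5 points is about 0.2 of a standard error.

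**4. Lack-of-efficacy stops coded as ICE-3.** If return to baseline means no response, own-arm imputation adds up to 45 points per masked subject on active drug and up to 15 on placebo. Both arms move, the active arm by more per subject.

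**The case against.** The strongest reply is that ICE-3 was meant as discontinuation for any remaining reason. Protocol 7.1 gives one list of reasons for stopping IP or leaving the study; adverse event, lack of efficacy and protocol deviation are all on it. SAP 7.8 introduces intercurrent events in terms of changes in treatment. Imputing ICE-3 as if treatment had continued makes little sense for a late visit, and one fixed code per patient suits a single discontinuation reason. On that reading neither problem arises. It is plausible, but the SAP does not state it, and it fits poorly with SAP 7.8 itself, which treats termination of the study by the sponsor, an item on that same Protocol list, as unrelated to the ICEs.

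Second, the fixed-code sentence stands in the primary-analysis section, while SAP 7.8 speaks of the occurrence of each ICE. Applying it to the sensitivity analysis is therefore an inference. It remains the only rule given for a subject with more than one event; 7.8.1.2.1 supplies no other.

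Third, SAP 7.8.1.2.4 counts missing histology as non-response. Protocol 7.1 requests an early-termination biopsy only for stops from Week 16, so an AE stop in Week 8 will often have none. That analysis is harsher than the control-based rule and does not depend on the ICE code. This is a real backstop, but it does not make the per-ICE analysis well defined.

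A reader might also infer that minor deviations void Week 24 biopsies throughout the trial. They do not. The primary analysis, the supportive analysis in subjects with both biopsies, and the analyses in 7.8.1.2.2 to 7.8.1.2.4 keep every observed biopsy.

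**Conclusion.** The point stands for the per-ICE sensitivity analysis and, more weakly, for the imputation of missing biopsies in the primary analysis. Followed literally, the stated rules discard observed biopsies after minor deviations and move some AE stops on active drug from control-based to own-arm imputation.

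The size is uncertain, because the documents give no deviation rate, AE-stop rate or overlap between them. Under the assumed shares, power in that sensitivity analysis falls from 94% to about 83% or 68% (30% or 50% set aside). The masking adds about 1.5 points to the 30 mg rate when 10% stop for AEs and half had an earlier deviation, or 3.0 if all did. Study success does not rest on this analysis, so the power loss measures its usefulness, not the trial's chance of success.

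Two stronger conclusions are not supported. The primary estimate from observed biopsies is not affected. Nor does a shift of about 0.2 of a standard error show that agreement between this analysis and the primary one is worthless. It shows that the check is less exact and somewhat more favourable than intended. The change is worth making before unblinding because the ambiguity is avoidable and the remedy is cheap.

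**What to change.** In SAP 7.8, 7.8.1.1 and Table 5:

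1. Define ICE-3 as IP discontinuation for any reason other than lack of efficacy or AE, plus the start of a Protocol 6.7.1 prohibited therapy classed as an important deviation in the blinded SAP 7.3 review. The existing exception for sponsor termination can stay, since it is imputed by the same model.
2. State that no other deviation is an intercurrent event.
3. Replace the fixed code with a precedence rule: discontinuation for AE or lack of efficacy overrides an earlier ICE-3. State that the rule applies to both the primary and the sensitivity analyses.
4. Make Table 5 agree with 7.8.1.2.1 that ICE-3 is imputed from the subject's own randomized arm; Table 5 now refers to the treatment arms collectively.

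A separate fourth category is not needed for imputation, because its handling would equal that of ICE-3. A flag for subjects who start a prohibited therapy is enough to report them separately.

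The cost is SAP wording and one derived flag from concomitant-medication data already collected. Protocol Section 9 gives the SAP precedence, so the change can be made there. The downside is that the blinded review must settle the qualifying deviations before the Week 24 unblinding.
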